4.4.2 Prohibited Therapy

Use of the following concomitant therapies is prohibited:

- Experimental agents or marketed HD agents at experimental doses that are being tested for the treatment of HD, including, but not limited to, cholinesterase inhibitors, memantine, amantadine, and riluzole
- Antiplatelet or anticoagulant therapy, including, but not limited to, aspirin (unless ≤ 81 mg/day), clopidogrel, dipyridamole, warfarin, dabigatran, rivaroxaban, and apixaban
- Sedation for lumbar puncture or IT bolus procedures in the study
Depending on institutional guidelines, local anesthesia is permissible for the lumbar puncture procedure
- Use of anti-anxiety medication is discouraged during scheduled MRI scans in the study. Anti-anxiety medication used to prevent movement disorder to allow successful MRI scan is not permitted in this study, as movement disorder too severe to scan under drug-free conditions is an overall study exclusionary criterion.

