4.5.5 Collection of Cerebrospinal Fluid (Lumbar Puncture Procedure)

Within 72 hours prior to performing each scheduled lumbar puncture, local laboratory analysis of coagulation factors (INR and/or PT, aPTT) and platelets must be conducted and the results reviewed. The lumbar puncture should be performed at approximately the same time at each visit (ideally in the morning between 8:00 a.m. and 12:00 noon or in the early afternoon between 12:00 noon and 3:00 p.m.) to minimize potential diurnal

variation of CSF parameters. CSF fluid (20 mL) is to be collected for analyses using a lumbar puncture collection kit. If there are difficulties in collecting 20 mL of CSF fluid, a minimum of 5 mL should be collected over a maximum of 60 minutes, once CSF flow has been established. The operator must confirm CSF flow is present prior to injecting drug. A 24G atraumatic needle, as specified in the LP procedure and CSF collection guidelines, should be used to minimize risk of post-lumbar puncture syndrome.

Sedation may not be used. Depending on institutional guidelines, local anesthesia should be used for the procedure. Spinal ultrasound may be used for the lumbar puncture procedure if deemed necessary, but ultrasound is not required. Ultrasound may be used if attempts at lumbar puncture without imaging are unsuccessful, if it is local practice to use ultrasound, or if institutional guidelines dictate use of ultrasound with each lumbar puncture. Fluoroscopy guidance can also be used, if local institutional guidelines dictate and local ECs and HAs have approved the use of the technique, but it is not required. Where fluoroscopy is used, patients should also be informed and consent obtained.

For details on the lumbar puncture and IT bolus dosing procedure, please refer to the LP procedure and CSF collection guidelines and instructional video. *Effective 22 March 2021, no further study treatment will be administered.*

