When applicable, study treatment administration will occur via a lumbar puncture using a needle inserted into the L3/L4 space, although placement at a different level (either in the space above or the space below) is allowed if patient anatomy or clinical judgment dictates. The left lateral position is mandatory in the first instance for the procedure for consistency of procedure practice across sites and within patients, unless patient-specific factors require use of the upright, sitting position or the physician/operator has pre-existing experience using LP/intrathecal bolus dosing in the sitting position and prefers the use of the upright sitting position, as guided by the patient, his or her judgment. Whichever position is used, once access is established to the IT space, the entire IT bolus procedure should be completed in the same position, to limit the risk of the needle losing position while the spinal needle is inserted. Subsequent LP administrations should occur using the same position.

Patients will be discouraged from resting supine after the lumbar puncture procedure and will be encouraged to mobilize immediately by walking around at a minimum and, if feasible, walking briskly for approximately 30 minutes, after which the postdose neurological examination can occur (*if study treatment was administered*). Patients should not perform any activity that is associated with a change in the ambient air pressure for at least 24 hours *post-LP procedure* (e.g., air travel, scuba diving, or hot air balloons).

Lumbar punctures will be performed as specified in the schedule of activities (see [Appendix 1](#)), with the last CSF sample obtained at the Week 101 end-of-treatment

visit. After discontinuation of study treatment, LPs will be performed at the ETT and EoT for ETT visits (see [Appendix 1a](#) and [Appendix 1b](#)). No study drug will be administered at these visits.

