5.1.1.2 Spinal Hematoma

Post-lumbar puncture spinal hematoma is a very rare but important potential risk that can present as persistent back pain, radicular pain, new sensory or motor symptoms, sphincter disturbance, or meningism. Prompt MRI scanning should be performed if suspicion of spinal hematoma arises. Patients with susceptibility to bleeding, patients with coagulopathy, and patients receiving anticoagulant therapy are at an increased risk of spinal hematoma and will be excluded from the study (see Section 4.1.2).

Management of spinal hematomas should include consultation with neurosurgical colleagues.

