^k Prior to performing each scheduled lumbar puncture, local laboratory analysis of coagulation factors (INR and/or PT, aPTT) and platelets must be conducted and the results reviewed. Collection for these local laboratory tests may occur at any time in the 72 hours prior to the lumbar puncture. The lumbar puncture should be performed at approximately the same time at each visit (ideally in the morning between 8:00 a.m. and 12:00 noon or in the early afternoon between 12:00 noon and 3:00 p.m.) to minimize potential diurnal variation of CSF parameters. CSF fluid (20 mL) is to be collected for analyses using a lumbar puncture collection kit. If there are difficulties in collecting 20 mL of CSF fluid, a minimum of 5 mL should be collected over a maximum of 60 minutes, once CSF flow has been established. A 24G atraumatic needle, as specified in the LP procedure and CSF collection guidelines, should be used. Depending on institutional guidelines, local anesthesia should be used for the procedure. Sedation may not be used. Spinal ultrasound may be used for the lumbar puncture procedure if deemed necessary, but is not required. Ultrasound guidance may be used if attempts at lumbar puncture without imaging are unsuccessful, if it is local practice to use ultrasound, or if institutional guidelines dictate use of ultrasound with each lumbar puncture. Patients will be discouraged from resting supine after the lumbar puncture procedure and will be encouraged to mobilize immediately by walking around at a minimum and, if feasible, walking briskly for approximately 30 minutes. Patients should not perform any activity that is associated with a change in the ambient air pressure for at least 24 hours post-LP procedure (e.g., air travel, scuba diving, or hot air balloons). In the case of a failed CSF collection procedure (e.g., due to an inadequate establishment of access to the IT space), a second attempt may occur up to 7 days after the originally scheduled attempt. For this additional visit, safety and tolerability evaluations on the day of LP administration will be performed, including a pre-procedure neurological examination, vital signs, and a review of adverse events and concomitant medication. If the second attempt occurs more than 3 days after the first attempt, local laboratory analysis of coagulation factors (INR and/or PT, aPTT) and platelets need to be conducted again and results reviewed prior to the LP attempt.

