Appendix 5 Guidelines for Order of Assessments

This guidance is in addition to what is mandated throughout this protocol, including from Section 4.5.9.

- Screening Visits: Screening assessments can be performed over several days through the 28-day screening period. Blood sample for CAG repeat testing and the MRI scans should be taken as early as possible to enable the results to be available in time for randomization. The electronic clinical outcome assessments (eCOAs) can be done after eligibility has been confirmed for all other parameters, so that patients and sites are not spending unnecessary time on eCOAs before knowing if the patient will fulfill all the other eligibility criteria.
- All eCOA blocks should always be done in a sequential order as per [Appendix 2](#), [Appendix 3](#), and [Appendix 4](#). One block cannot be done before the previous block is completed (i.e., the blocks should be completed sequentially as Block 1, Block 2, Block 3, Block 4, and Block 5).
- Within a block, the protocol order should be kept to prevent bias. All the assessments have been ordered by importance for the primary and secondary study endpoints.
- eCOA blocks can be split over 2 consecutive days. When eCOA blocks are split over 2 consecutive days, Blocks 1 and 2 should always be completed together on the same day. As such, either Blocks 1–5 or just 1 and 2 can be done the day before dosing.
- The same methodology should be kept for an individual patient's eCOAs, to prevent intra-patient variability. For example, if the blocks are done all together, they should be performed that way for all visits, but at a minimum for baseline and Week 101 visits.
- The same timings should be kept for each patient's eCOAs at each visit, but especially for Day 1 and Week 101 visits.
- Blood sampling (all or just coagulation) can be done before Block 1 or after Block 5 or between blocks, but only as follows:
 - The eCOAs are separated into 2 consecutive days
 - The blood sampling should be done after Block 2 but should not be done before Block 3 on the following day.

Therefore, blood sampling can occur the day before (before Block 1, after Block 2, or after Block 5) depending on which eCOAs are done the day before dosing. Alternatively, blood sampling can be done before Block 1 on the day of dosing. Again the same methodology should be used for the patient throughout the study but in particularly for the Day 1 and Week 101 visits.

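### The re-test rule for a repeat lumbar puncture counts from the failed attempt, not from the blood draw, so a repeat can rest on clotting and platelet results older than 72 hours

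*Protocol*

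**What the plan says.** **Scheduled punctures.** Section 4.5.5 sets the limit: "Within 72 hours prior to performing each scheduled lumbar puncture, local laboratory analysis of coagulation factors" and platelets must be done and reviewed. Appendix 1a footnote x and Appendix 1b footnote k leave the draw free within that window: "Collection for these local laboratory tests may occur at any time in the 72 hours prior to the lumbar puncture". Appendix 5 gives narrower practical guidance, placing blood sampling on the day before dosing or on the day itself.

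**Repeat punctures.** If dosing or CSF collection fails, a second attempt may follow up to 7 days after the scheduled one. The tests must then be redone on this condition: "If the second attempt occurs more than 3 days after the first attempt, local laboratory analysis of coagulation factors" and platelets. The same condition stands in the synopsis, Section 3.1.1, Appendix 1a footnote x and Appendix 1b footnote k. For the repeat visit itself, Appendix 1b footnote k says: "For this additional visit, safety and tolerability evaluations on the day of LP administration will be performed, including a pre-procedure neurological examination, vital signs", plus a review of adverse events and concomitant medication. Clotting tests and platelets are not named there.

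**Still in force.** Section 4.5.5, as amended in Version 6: "After discontinuation of study treatment, LPs will be performed at the ETT and EoT for ETT visits". Appendix 1b applies to all patients from 22 March 2021 and carries the repeat-attempt rule for failed CSF collection.

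**The concern.** The two rules protect against the same hazard but measure time from different origins. The 72-hour limit runs from the blood draw to the needle. The 3-day trigger runs from the first needle to the second. Since 3 days equals 72 hours, the second rule looks meant to mirror the first, but it does so only if the blood was drawn at the time of the first attempt.

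The protocol does not say outright that a repeat within 3 days needs no new test. That follows from the condition: if fresh tests were needed at every repeat, the 3-day threshold would have no function. A site in full compliance could thus puncture on results that would not be accepted for a scheduled LP. The check is mandatory because of spinal hematoma, which Section 5.1.1.2 describes so: "Post-lumbar puncture spinal hematoma is a very rare but important potential risk". That section also names coagulopathy and susceptibility to bleeding as risk factors.

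**Working it through.** This is interval arithmetic; no sample size, power or alpha figure is involved.

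**Inputs**
- *a* = age of the sample at the first attempt: 0 to 72 h (Section 4.5.5; Appendix 1a footnote x; Appendix 1b footnote k). Under Appendix 5 sampling, about 0 to 24 h.
- *g* = gap from first to second attempt: up to 7 days allowed; no re-test triggered while *g* ≤ 3 days = 72 h.

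**Formula**

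Age of result at the repeat = *a* + *g*. The 72 h limit is exceeded whenever *a* + *g* > 72 h.

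**Results without a re-test**

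| Sample drawn before first attempt (*a*) | Repeat at 24 h | Repeat at 48 h | Repeat at 72 h |
|---|---|---|---|
| 0 h (same day) | 24 h | 48 h | 72 h |
| 24 h (day before) | 48 h | 72 h | **96 h** |
| 48 h | 72 h | **96 h** | **120 h** |
| 72 h (footnote maximum) | **96 h** | **120 h** | **144 h** |

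Bold cells exceed 72 h. The maximum is 72 + 72 = 144 h (6 days), twice the limit for a scheduled LP. Within the Appendix 5 guidance only one cell exceeds it: a day-before draw with a 3-day repeat, 24 + 72 = 96 h, an excess of 24 h.

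If 3 days is read as calendar days, with both attempts inside the ideal 8:00 a.m. to 3:00 p.m. window, the gap can reach 72 + 7 = 79 h and the maximum age 72 + 79 = 151 h.

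**With a trigger based on sample age** (re-test if *a* + *g* > 72 h), the maximum at any LP, first or repeat, is 72 h. Because *a* ≥ 0, any gap over 72 h already means a sample over 72 h old, so the new trigger catches every case that the present one catches.

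**The case against.** **The 72-hour rule is written for scheduled punctures, so nothing is contradicted.** A repeat may be meant to have its own, looser rule. If the repeat instead counts as scheduled, a site can satisfy both rules by re-testing whenever either limit is passed. This has some force: strict contradiction is avoidable. But on the first reading older results are permitted with no reason given, and on the second the 3-day trigger misleads the site about when to re-test.

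**Other text may require fresh tests.** Section 3.1.1 refers to the schedules in Appendices 1a and 1b, which have a row for local clotting tests and platelets, and the list of evaluations at the repeat visit is introduced as non-exhaustive. Section 5.1.2.3 says platelets are monitored at each visit before LP. However, the schedule rows carry the same footnotes that contain the 3-day condition, and the platelet sentence does not cover INR, PT or aPTT. Reading either as requiring new tests at every repeat would make the specific condition pointless.

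**The clinical consequence is slight.** This stands. Section 4.1.2 excludes bleeding disorders and low platelets. Section 4.4.2 prohibits the drugs of most concern: "Antiplatelet or anticoagulant therapy, including, but not limited to, aspirin" above 81 mg/day. Medication is reviewed at the repeat visit, and Section 5.1.2.3 reports no clinically significant fall in platelets in the program. Nothing in the protocol shows that a 96-hour result is less safe than a 72-hour one. The 144 h figure needs both intervals at their limits.

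**The separate LP guidelines may already deal with repeats.** They were not available, so this cannot be ruled out; it would not correct the protocol text.

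**Conclusion.** The point holds. The re-test trigger is tied to the wrong starting time, and the written rule lets a repeat LP go ahead on clotting and platelet results older than 72 hours: about 96 hours under the sampling that Appendix 5 describes, and 144 hours at the extreme. It is not always so; a same-day draw with a repeat within 72 hours stays inside the limit.

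The conclusion rests on reading the conditional sentence as exempting repeats within 3 days. How many patients would be affected cannot be estimated, since the LP failure rate is not stated. After 22 March 2021 at most two scheduled LPs per patient remain (the ETT visit and the Week 101 EoT for ETT visit). This is a procedural safety point of small absolute risk, with no bearing on endpoints, estimand, power or type I error. It is worth correcting because the check is mandatory and the correction is simple.

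**What to change.** In the synopsis, Section 3.1.1, Appendix 1a footnote x and Appendix 1b footnote k, replace the 3-day condition with one based on sample age:

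> If the most recent coagulation and platelet sample will be more than 72 hours old at the second attempt, the tests must be repeated and the results reviewed before the LP attempt.

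Section 4.5.5 has no sentence on repeat attempts and needs no change.

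The cost is one sentence in four places and an occasional extra local INR and/or PT, aPTT and platelet test, which sites already run before each LP. As a protocol change it needs approval under Section 9.7 and has to reach about 110 sites (Section 9.5). Given the small risk, it can go into the next amendment.

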5.3.1 Adverse Event Reporting Period

Investigators will seek information on adverse events at each patient contact. All adverse events, whether reported by the patient or noted by study personnel, will be recorded in the patient's medical record and on the Adverse Event eCRF.

After informed consent has been obtained but prior to initiation of study drug, only serious adverse events caused by a protocol-mandated intervention (e.g., invasive procedures such as biopsies, discontinuation of medications) should be reported (see Section 5.4.2 for instructions for reporting serious adverse events).

After initiation of study drug, all adverse events will be reported until 5 months after the final dose of study drug or until the patient receives his or her first dose in the OLE study (BN40955), at which time reporting will occur per the new study requirements. *For patients consented to version 6 of the protocol, who have discontinued study treatment and have entered the ETT schedule of assessments, AEs will be reported until 5 months after the last dose of study drug or until the EoT for ETT Week 101 visit (whichever is longer). For patients consented to version 6 of the protocol, who have received their last dose of study treatment less than 5 months before the scheduled Week 101 EoT for ETT visit, an additional safety telephone call should be performed 5 months after the last dose.*

Instructions for reporting adverse events that occur after the adverse event reporting period are provided in Section 5.6.

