5.4.2.2 Events That Occur after Study Drug Initiation

After initiation of study drug, serious adverse events and adverse events of special interest will be reported until 5 months after the final dose of study drug *or until the EoT for ETT Week 101 visit (whichever is longer)*. Investigators should record all case details that can be gathered immediately (i.e., within 24 hours after learning of the event) on the Adverse Event eCRF and submit the report via the electronic data capture (EDC) system. A report will be generated and sent to Roche Safety Risk Management by the EDC system.

In the event that the EDC system is unavailable, the paper Clinical Trial Serious Adverse Event/Adverse Event of Special Interest Reporting Form provided to investigators should be completed and submitted to the Sponsor or its designee immediately (i.e., no more than 24 hours after learning of the event), either by faxing or by scanning and emailing the form using the fax number or email address provided to investigators. Once the EDC system is available, all information will need to be entered and submitted via the EDC system.

Instructions for reporting serious adverse events that occur >5 months after the final dose of study treatment are provided in Section 5.6.

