5.6 ADVERSE EVENTS THAT OCCUR AFTER THE ADVERSE EVENT REPORTING PERIOD

The Sponsor should be notified if the investigator becomes aware of any serious adverse event that occurs after the end of the adverse event reporting period (defined as greater than 5 months after the final dose of study drug), if the event is believed to be related to prior study drug treatment. These events should be reported through use of the Adverse Event eCRF. However, if the EDC system is not available, the investigator should report these events directly to the Sponsor or its designee, either by faxing or by

scanning and emailing the paper Clinical Trial Serious Adverse Event/Adverse Event of Special Interest Reporting Form using the fax number or email address provided to investigators.

5.7 EXPEDITED REPORTING TO HEALTH AUTHORITIES, INVESTIGATORS, INSTITUTIONAL REVIEW BOARDS, AND ETHICS COMMITTEES

The Sponsor will promptly evaluate all serious adverse events and adverse events of special interest against cumulative product experience to identify and expeditiously communicate possible new safety findings to investigators, IRBs, ECs, and applicable health authorities based on applicable legislation.

To determine reporting requirements for single adverse event cases, the Sponsor will assess the expectedness of these events using the following reference document:

- RO7234292 Investigator's Brochure

The Sponsor will compare the severity of each event and the cumulative event frequency reported for the study with the severity and frequency reported in the applicable reference document.

Reporting requirements will also be based on the investigator's assessment of causality and seriousness, with allowance for upgrading by the Sponsor as needed.

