- × CSF samples will be obtained at the Week 101 EoT, *Week 101 EoT for ETT, and ETT visits*, but no study drug will be administered.
- × Patients in Q16W arm will receive placebo at these visits.

^{aa} Medication (e.g., prescription drugs, over-the-counter drugs, vaccines, herbal or homeopathic remedies, nutritional supplements) used by a patient in addition to protocol-mandated treatment from screening to the study completion/discontinuation visit.

^{bb} After informed consent has been obtained but prior to initiation of study drug, only serious adverse events caused by a protocol-mandated intervention should be reported. After initiation of study drug, all adverse events will be reported until 5 months after the final dose of study drug. After this period, all deaths, regardless of cause, should be reported. In addition, the Sponsor should be notified if the investigator becomes aware of any serious adverse event that is believed to be related to prior study drug treatment.

^{cc} The DCL will be assessed at screening only (i.e., without the full TMS assessment). The TMS scale will be assessed (excluding the DCL) at all other timepoints.

^{dd} Excluding MRIs, which have a visit window of -14 to -7 days.

^{ee} During the treatment period, a safety follow-up telephone call will be conducted for the months in which no clinic visits are. A safety follow-up call will also be conducted approximately 2 months after the Week 101 visit. Telephone safety follow-up calls will assess any changes to ongoing adverse events or occurrence of new adverse events and changes to concomitant medication. Unscheduled visits can occur based on the outcome of this safety follow-up call.

Appendix 1b Schedule of Activities for Early Treatment Termination (Applicable to all Patients from 22 March 2021)

Visit	ETT ^a	FU Week 53 ^a	FU Week 69 ^a	EoT for ETT (Week 101) ^a	Safety Follow-Up Calls ^b
Month		13	17	25	
Window (days)	≤ 56 days after the decision to discontinue study treatment	(± 7)	(± 7)	(± 7) ^c	(± 7)
Vital signs ^d	x				
Complete physical examination ^e	x				
Neurologic examination ^f	x			x	
ECG ^g	x			x	
Hematology ^h	x			x	
Chemistry ⁱ	x			x	
Pregnancy test ^j	x			x	
Local INR and/or PT, aPTT, platelet count ^k	x			x	
Urinalysis ^l	x			x	
Plasma sample for PK	x				
Plasma sample for immunogenicity testing	x			x	
Plasma sample for biomarkers	x			x	
CSF sample for safety/biomarkers	x			x	
MRI ^m				x	
Independence Scale	x	x	x	x	
MoCA	x	x	x	x	

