- ^u Medication (e.g., prescription drugs, over-the-counter drugs, vaccines, herbal or homeopathic remedies, nutritional supplements) used by a patient in addition to protocol-mandated treatment from screening to the study completion/discontinuation visit.*
- ^v All adverse events will be reported until 5 months after the final dose of study drug. After this period, all deaths, regardless of cause, should be reported. In addition, the Sponsor should be notified if the investigator becomes aware of any serious adverse event that is believed to be related to prior study drug treatment (see Section 5.6).*

Appendix 2 Clinician-Reported Outcomes for Patients Enrolled after Implementation of Protocol Version 4

Assessment	Name	Items	Concepts	Approx. Duration	Timing
FA	UHDRS Functional Assessment	25	Daily function	15 min	Baseline and Weeks 5, 21, 37, 53, 69, 85, and 101 and ETT visits
IS	Independence Scale	1	Functional disability	3 min	Screening, baseline, and Weeks 5, 21, 37, 53, 69, 85, and 101 and ETT visits
TFC	Total Functional Capacity Scale	5	Overall function	10 min	Baseline and Weeks 5, 21, 37, 53, 69, 85, and 101 and ETT visits
TMS	Total Motor Score	31	Motor function	15 min	DCL only: Screening TMS without DCL: Baseline and Weeks 5, 21, 37, 53, 69, 85, and 101 and ETT visits
C-SSRS	Columbia-Suicide Severity Scale	5	Suicidal ideation and behavior	20 min full version; 5 min follow-up version	Full version at screening in clinic; follow-up version at baseline and all post-baseline clinic visits
CGI-S	Clinical Global Impression, Severity	1	Overall severity of patient status	2 min	Baseline and Weeks 5, 21, 37, 53, 69, 85, and 101 and ETT visits
CGI-C	Clinical Global Impression, Change	1	Overall change in patient status	2 min	Weeks 5, 21, 37, 53, 69, 85, and 101 and ETT visits
HD-DAS	Huntington's Disease Daily Activities Scale	25	Daily function	25 min	Screening and Weeks 13, 29, 45, 61, 77, and 93

DCL=diagnostic confidence level.

**Appendix 3 Patient-Reported, Observer-Reported, and Performance Outcomes
and Roche HD Mobile Application for Patients Enrolled after Implementation of Protocol
Version 4**

Assessment	Name	Items	Concepts	Approx. Duration (min)	PRO, ObsRO, PerfO, Behavior	Timing	Location
AES	Apathy Evaluation Scale	18	Apathy	10	PRO + ObsRO	Baseline and Weeks 13, 29, 45, 61, 77, 93, and 101	In-clinic

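### Adverse event reporting ends at two different times in the current protocol: Section 5.3.1 runs it to Week 101, while four other passages stop it five months after the last dose

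*Protocol*

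**What the plan says.** Two passages carry reporting to Week 101:

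- **Section 5.3.1**, for patients who consented to version 6 and are on the ETT schedule: "AEs will be reported until 5 months after the last dose of study drug or until the EoT for ETT Week 101 visit", with the longer of the two governing. The same section ends reporting at the first open-label extension (OLE) dose for patients who enter that study.
- **Section 5.4.2.2**, for serious adverse events and events of special interest: five months after the final dose "or until the EoT for ETT Week 101 visit (whichever is longer").

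Four passages keep a plain five-month limit:

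- **Appendix 1b, footnote v**, attached to the adverse events row of the ETT schedule: "All adverse events will be reported until 5 months after the final dose of study drug". After that it asks for all deaths, and for serious events believed related to earlier study drug.
- **Appendix 1a, footnote bb**: "After initiation of study drug, all adverse events will be reported until 5 months after the final dose of study drug", with the same provision for deaths and related serious events.
- **Section 5.6**, which refers to "the end of the adverse event reporting period (defined as greater than 5 months after the final dose of study drug") and beyond that point asks only for serious events believed related. It does not mention deaths.
- **Section 5.4.2.2, closing sentence**: "Instructions for reporting serious adverse events that occur >5 months after the final dose of study treatment are provided in Section 5.6".

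Appendix 1b also marks adverse events at the ETT, Week 53, Week 69 and Week 101 visits. Its footnote b has calls every 8 weeks between visits ask about new and ongoing events and enter them in the eCRF, with no five-month limit.

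**The concern.** Patients remain in the study without treatment so that safety and efficacy outcomes can be followed to Week 101. Incidence and severity of adverse events is the first safety endpoint listed in Section 2.2, and Section 6.7 summarizes it by preferred term, severity and relationship. If about 110 sites (Section 9.5) read the reporting period differently, the late part of that record will be complete at some sites and thin at others, and off-treatment incidence will be hard to interpret.

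Appendix 1b is the schedule that sites work from for every remaining patient. A site that stopped recording at five months would be following footnote v as written. Past that point, whether a non-fatal serious event is reported would depend on a relatedness judgment, which the Section 5.3.1 rule does not require before Week 101.

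**Working it through.** There is no plan figure to reproduce. The check compares the passages and measures the gap between the two rules.

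**Passages side by side**

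| Passage | Reporting ends | Asked for after five months, before Week 101 |
|---|---|---|
| 5.3.1 | Later of 5 months or Week 101 | All adverse events |
| 5.4.2.2, main text | Later of 5 months or Week 101 | All serious events and events of special interest |
| 5.4.2.2, closing sentence | Refers serious events after 5 months to 5.6 | As in 5.6 |
| 5.6 | 5 months | Serious events believed related |
| Appendix 1a, footnote bb | 5 months | All deaths; serious events believed related |
| Appendix 1b, footnote v | 5 months | All deaths; serious events believed related |
| Appendix 1b, adverse events row and footnote b | No five-month limit | Events at Weeks 53, 69 and 101 and at 8-weekly calls |

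Section 5.4.2.2 and Appendix 1b are each inconsistent within themselves. Deaths are handled unevenly as well: Section 5.3.5.8 sends deaths after the reporting period to Section 5.6, which is silent on them, while footnotes v and bb ask for all of them.

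**Size of the gap**

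Inputs: *w*, the week of the last dose, taken from the dosing visits in Table 1 (Day 1, Day 29, then every 8 weeks from Week 13 to Week 93); end of follow-up at Week 101; *m*, five months in weeks. The protocol does not convert months to weeks, so two values are used: 20 weeks (the schedule's 4-week months) and 5 × 365.25 / 12 / 7 = 21.74 weeks (calendar months).

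- Off-treatment time = 101 − *w*
- Time outside the five-month window = max(0, 101 − *w* − *m*)

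| Last dose (week) | Off treatment (weeks) | Outside window, *m* = 20 | Outside window, *m* = 21.74 |
|---|---|---|---|
| 1 | 100 | 80 (80%) | 78.3 (78%) |
| 13 | 88 | 68 (77%) | 66.3 (75%) |
| 29 | 72 | 52 (72%) | 50.3 (70%) |
| 45 | 56 | 36 (64%) | 34.3 (61%) |
| 53 | 48 | 28 (58%) | 26.3 (55%) |
| 61 | 40 | 20 (50%) | 18.3 (46%) |
| 69 | 32 | 12 (38%) | 10.3 (32%) |
| 77 | 24 | 4 (17%) | 2.3 (9%) |
| 85 | 16 | 0 | 0 |
| 93 | 8 | 0 | 0 |

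The rules differ only when *w* < 101 − *m*, that is, before Week 81 (or 79.3). More than half of off-treatment time falls outside the window only when *w* < 101 − 2*m*, that is, before Week 61 (or 57.5).

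The distribution of last-dose weeks is not in the protocol. As an assumption only, equal weight on every dosing visit puts 64-66% of off-treatment time outside the window. Restricting to visits from Week 29 gives 51-54%, from Week 45 41-45%, and from Week 61 26-30%. With the Section 5.3.1 rule in all passages the gap is zero for every *w*.

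**The case against.** The strongest answer is that the governing text can be identified. Section 5.3.1 is the section on the reporting period, it addresses this group of patients specifically, and Section 5.3.5.8 defers to it. The protocol's change summary names Sections 5.3.1 and 5.4.2.2 as the places where the period was clarified. Collection also continues: events are to be sought at each patient contact, marked at the Week 53, 69 and 101 visits, and documented from the 8-weekly calls. On this view it is an edit not carried through to every passage. That description is fair, but footnote v sits on the adverse events row itself and sets a limit, so a site following it is not deviating from the protocol.

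A reader might infer that most off-treatment safety follow-up would be lost. The documents do not support that. Whether more than half of the time is affected depends on last-dose timing, which is not given, and for last doses at Weeks 85 and 93 nothing is affected. The content at risk is also narrower than safety follow-up. Related serious events remain reportable under every passage, and the appendix footnotes keep all deaths. Week 101 neurologic examination, ECG, laboratory tests, CSF, MRI, MoCA and C-SSRS stay scheduled.

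A reader might also infer a biased comparison between arms. Site staff and patients remain blinded (Section 4.2), and nothing in the protocol makes the ambiguity differ by arm. Table 5 treats an event as related unless stated criteria point elsewhere, which softens the dependence on causality judgment. Nor should the stop be presented as a response to a new safety signal: Section 1.3 says it was not, and cites unfavorable trends in both safety and efficacy.

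**Conclusion.** The conflict stands, and it lies in current text. Sites following the five-month passages could omit non-serious adverse events and serious events not believed related for 0% to about 80% of a patient's off-treatment time, depending on the week of the last dose. The upper end applies to a last dose at the start of treatment and is a bound, not an estimate for the trial. The range rests on follow-up to Week 101 and on five months being 20 to 21.7 weeks.

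The consequence is incomplete and uneven capture across sites in the late off-treatment period. The primary efficacy analysis is untouched. Because events not recorded at the time are hard to recover fully, the correction is best made while follow-up is running.

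**What to change.** - In Appendix 1b footnote v, Appendix 1a footnote bb, the definition in Section 5.6 and the closing sentence of Section 5.4.2.2, replace the five-month cut-off with a reference to the reporting period defined in Section 5.3.1.
- Use a cross-reference and do not paste the Week 101 wording. Section 5.6 is not confined to ETT patients, and pasting would drop the version 6/ETT condition and the separate end point for OLE entrants.
- State one rule for deaths after the reporting period, and use it in Sections 5.3.5.8 and 5.6 and in both footnotes.
- Notify sites of the period that applies, and ask them to enter any events left out under the shorter reading.

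The cost is four cross-reference edits, the aligned wording on deaths and a site letter. No visit, call or procedure is added. Under Section 9.7 the change needs ethics and regulatory approval as locally required, unless it qualifies as administrative.
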